16.12. Record Retention

The sponsor and investigator will retain all records and documents pertaining to this study. They will be available for inspection by the appropriate regulatory agencies. In addition, the investigator will retain the source documents from which the information entered on the eCRF was derived. These records are to be retained in a secure storage facility maintained by the investigational center for 10 years after completion of the study or termination of the study, whichever is longer. The investigator should not dispose of these records without the approval of the sponsor. The investigator should take measures to prevent accidental or early destruction of the clinical study related materials. The sponsor shall keep the clinical data indefinitely and till no such medical device is used.

16.13. Suspension or Early Termination of Clinical Study

16.13.1. Investigational Center suspension or termination

Medtronic, EC, or a regulatory authority may decide to suspend or prematurely terminate an Investigational Center (e.g. if information becomes available that the risk to study subject is higher than initially indicated, business decision, in case of expiring approval of the reviewing EC, non-compliance to

the CIP or lack of enrollment). The medical device clinical trial management departments of clinical trial institutions should be notified within 5 days with the rationale in writing. If an Investigational Center is suspended or prematurely terminated, Medtronic shall promptly inform the investigator(s) of the termination or suspension and the reason(s) for this. The investigator shall then promptly inform the reviewing EC and the study subjects.

When the risks are found to outweigh the potential benefits or when there is conclusive proof of definite outcomes, investigators must assess whether to continue, modify or immediately stop the clinical study in the respective Investigational Center and immediately inform the sponsor, EC, and department of food and drug administration of the concerned province, region and municipality.

The suspended clinical studies cannot be resumed without permission from EC. Upon completion of clinical studies, the applicant shall send written notice to the management of food and drug administration of the concerned province, autonomous region and municipality

16.13.2. Subject follow-up in case of termination

In case of early investigational center suspension or termination, all subjects should be contacted to plan an early Termination visit at the Investigational Center. All efforts will be made to complete and report all study observations at the time of termination. The subject will return the study devices to the investigational center (unless subject is allowed to keep them per country requirement), receive appropriate treatment and follow-up.

16.14. Study close out

At the time of a study close-out, the investigators will be notified by Medtronic. Appropriate notification/report to EC and regulatory authority will be provided, if required per local laws and regulations.

18.3. Appendix C: Relevant qualification document(s) of the Sponsor/Local Sponsor(Agent)

Relevant qualification document(s) of the Sponsor/Local Sponsor(Agent) will be provided under a separate cover.

18.4. Appendix D: Informed Consent Form Template

The ICF template will be provided under a separate cover.

19. Version History

Version	Summary of Changes	Author(s)/Title
A	
○ Not Applicable, New Document.	[REDACTED]
B	
○ See "CIP313 Summary of Protocol Changes_ Version A to B"	[REDACTED]

7.11	Device Deficiencies and Subject Feedback.....	20
7.12	Health Outcomes Analyses	20
7.13	Changes to Planned Analysis	20
8.	Validation Requirements.....	20
9.	Mock Tables, Listings and Figures	20
	See SAP appendix tables, listings and figures.....	20

1. Version History

Version	Summary of Changes	Author(s)/Title
V1.0	Not applicable	[REDACTED]

2. List of Abbreviations and Definitions of Terms

Abbreviation	Definition
A1C	Glycosylated hemoglobin
AE	Adverse Event
ARD	Absolute Relative Difference
BG	Blood Glucose
BMI	Body Mass Index
CEC	Clinical Events Committee
CFDA	China Food and Drug Administration
CGM	Continuous Glucose Monitoring
CGMS	Continuous Glucose Monitoring System
CIP	Clinical Investigation Plan
CTA	Clinical Trial Approval
CV	Curriculum Vitae
DKA	Diabetic Ketoacidosis
EC	Ethics Committee
eCRF	Electronic Case Report Form
EGA	Error Grid Analysis
ER	Emergency Room
EOS	End of Study
FST	Frequent Sample Testing
Hct	Hematocrit
ICF	Informed Consent Form
ISIG	Interstitial Signal
IV	Intravenous
MARD	Mean Absolute Relative Difference
OC-RDC	Oracle Clinical Remote Data Capture
PC	Personal Computer
POC	Point of Care
QC	Quality Control
SAE	Serious Adverse Event
SGV	Sensor Glucose Value

SID	Subject Identification
SMBG	Self-Monitoring of Blood Glucose
SQ	Subcutaneous
SSL	Secure Socket Layer
UADE	Unanticipated Adverse Device Effect
USB	Universal Serial Bus
YSI	Yellow Springs Instrument

CareLink™, CGMS™, Enlite™, iPro™, and MiniMed™ are trademarks of Medtronic plc.

CONTOUR® is a registered trademark of Ascensia Diabetes Care.

YSI™ is a trademark of Xylem Inc. or one of its subsidiaries.

3. Introduction

The iPro2 recorder is intended to continuously record interstitial glucose levels in persons with diabetes mellitus. This information is intended to supplement, not replace, blood glucose (BG) information obtained using standard home glucose monitoring devices. The information collected by the iPro2 recorder may be downloaded to a computer and reviewed by healthcare professionals. The information may allow identification of patterns of glucose-level excursions above and below a desired range, facilitating therapy adjustments, which may minimize these excursions.

The study is designed to demonstrate the performance of the Enlite Sensors used with the iPro2 when inserted in the abdomen of subjects ages 14 – 75 years and used for 6 days.

Accuracy data will be calculated based on comparing values from the iPro2 and Enlite Sensor to a “gold standard” (Yellow Springs Instrument [YSI™] plasma glucose values) in subjects during YSI frequent sample testing (FST). YSI glucose analyzers have been recognized standards for the measurement of BG and will be utilized across the investigational centers for the tests.

The purpose of this study is to demonstrate the performance and safety of the Enlite Sensor over 6 days when inserted in the abdomen and used with the iPro2 in subjects age 14 – 75 years.

This document provides details of the statistical analysis plan (SAP) for the clinical trial of evaluating the performance and safety of the Enlite Sensor over 6 days when inserted in the abdomen and used with the iPro2 in subjects age 14 – 75 years. The statistical analysis report will be issued for registration and declaration after the subjects complete study or terminate the trial early and the database is locked. See the table, listing and figure in the statistical analysis plan.

4. Study Objectives

The primary objective of the study is to demonstrate the accuracy of Enlite Sensor when connected to iPro2 when used over a period of 6 days.

5. Investigation Plan

5.1 Study Design

This study is a multi-center, randomized, prospective single-sample correlational design without controls. Up to 72 subjects will be enrolled in order to have approximately 60 subjects complete the study. Three investigational centers in China will be used during this study.

Each subject will wear the following devices:

- Two Enlite Sensors each connected to an iPro2 for approximately 6 days

Sensor Location:

- The 2 Enlite Sensors will be worn in the abdomen area. Investigational center staff will insert sensors and connect to the iPro2s.

During the study, each subject will be randomized and undergo one Yellow Springs Instrument (YSI™) frequent sample testing (FST) (Day 1, 3-4, or 6).

On the evening prior to FST, subjects will be asked to fast for approximately 12 hours and adjust their insulin and medications according to routine care (for example as they would do for fasting lipid panel). Subjects may fast for shorter period of time **based on investigator discretion**.

The subject should be in fasting status upon arrival hospital to start FST process. **The feeding protocol may be modified based on investigator discretion**. The duration of FST will be approximately 7 hours.

During the study, subjects will continue with their current diabetes regimen independent of the study devices. Subjects will be instructed by the investigational center that they are not to use the study devices (except for the study meter) for the management of their diabetes. The Study Meter may be used for treatment decisions and calibration of Enlite Sensor.

Fingerstick Testing: A minimum of 4 fingerstick glucose readings per day will be requested for subjects. Subjects should test prior to meals and at bedtime.

5.2 Primary Endpoint

The primary endpoint is 20/20% consistency evaluation with the reference value which is expressed by the agreement rate.

Sensor values from primary sensor will be compared to YSI plasma glucose values during YSI FSTs to analyze the agreement rate. Consistency rate = A + B:

A = (the number of pairs of the deviation of sensor value from primary sensor minus YSI value is within $\pm 20\%$ /total number of pairs) * 100% (when the blood glucose concentration is greater than 4.4 mmol/L (80 mg/dL), percentage of results with deviations from the reference value within $\pm 20\%$);

B = the number of pairs of the deviation of sensor value from primary sensor minus YSI value is within ± 20 mg/dL /total number of pairs) * 100% (when the blood glucose concentration is less than or equal to 4.4 mmol/L (80 mg / dL), percentage of results with deviations from the reference value within ± 1.1 mmol/L (20mg/dL).

5.3 Secondary Endpoints

The secondary endpoints are including mean absolute relative difference (MARD), mean rate in Zone A+B of Clarke Error Grid and Consensus Error Grid.

The MARD is calculated by the following formula:

$$ARD_k = 100\% \frac{|y_{CGM}(t_k) - y_{ref}(t_k)|}{y_{ref}(t_k)}$$

$$MARD = \frac{1}{N} \sum_{k=1}^N ARD_k$$

5.4 Inclusion and Exclusion Criteria

Inclusion Criteria:

1. Subject is 14 - 75 years of age at time of screening
2. Subject has a clinical diagnosis of type 1 or 2 diabetes as determined via medical record or source documentation by an individual qualified to make a medical diagnosis
3. Subject has adequate venous access as assessed by investigator or appropriate staff
4. Subject is willing to follow the study procedures and willing to come to study visits.
5. Subject is willing to perform at least 4 self-monitoring of blood glucose (SMBG) per day for 6 days

Exclusion Criteria:

1. Subject will not tolerate tape adhesive in the area of Enlite Sensor placement as assessed by qualified individual.
2. Subject has any unresolved adverse skin condition in the area of study device or device placement (e.g., psoriasis, rash, *Staphylococcus* infection)
3. Subject is actively participating in an investigational study (drug or device) wherein they have received treatment from an investigational study (drug or device) in the last 2 weeks
4. Subject is female and has a positive pregnancy screening test
5. Females of child bearing age and who are sexually active should be excluded if they are not using a form of contraception deemed reliable by investigator
6. Subject is female and plans to become pregnant during the course of the study
7. Subject has a hematocrit (Hct) lower than the normal reference range

Subject may not be on the research staff of those performing this study

5.5 Study Timeline

The subject's participation from study start to completion is approximately 1 – 3 weeks (including replacement sensor wear and repeat in clinic procedures).

Additional rescheduled visits could occur if Enlite Sensors dislodge and new Enlite Sensors must be re-inserted.

- Visit 1: Consent and Screening
- Visit 2: Randomization
 - Visit 1 and 2 can be combined, however all eligibility criteria on Visit 1 should be met, including review of Hct prior to Visit 2.
 - Visit 1 and Visit 2 should be no more than 2 weeks apart.
- Visit 3: Study Training and iPro2 Placement & Sensors Insertion
 - Two Enlite Sensors each connected to an iPro2
 - Dispense Patient Log Sheet
- Visit 4: YSI FST.
 - Study training and iPro2 placement & sensors insertion (Day 1 subjects who have not already received study training and iPro2 placement and sensor insertion from Visit 3)
 - Subjects will undergo one YSI FST on any one of the following sensor wear days:
 - Day 1 (1 – 25 hours)
 - Day 3 – 4 (49 – 97 hours)
 - Day 6 (121 – 145 hours)
- Visit 5: End of Study (EOS) Visit
 - iPro2 removed (**Please note that the subject should target wearing the device for 145 hours or longer from time of insertion**)
 - Investigational center staff will:
 - Download the iPro2 data from CareLink iPro following completion of the study devices wear
 - Obtain subject's Study Meter BG values and enter into CareLink iPro
 - Collect subject's Patient Log Sheet
 - Provide iPro2 data to sponsor
 - Return study devices
 - Subject complete questionnaires
 - Random assignment for primary sensor and secondary sensor via RDC

Guidelines for Combining Visits:

- All subjects meeting eligibility criteria:

- Visit 1 and 2 can be combined, however all eligibility criteria on Visit 1 should be met, including review of Hct prior to Visit 2.
- Subjects randomized to FST Day 1
 - Subjects doing FST on Day 1 may combine Visit 2 and Visit 3 as long as they are able to perform Visit 4 FST in the second half of FST day.
 - For example, subject does Visit 1 and 2 in the morning and performs Visit 3 in the afternoon. Subjects comes in the next day for Visit 4 in the morning within approximately 25 hours from time of insertion.
- Subjects randomized to FST Day 3-4
 - May combine Visit 2 and Visit 3
- Subjects randomized to FST Day 6
 - May combine Visit 2 and Visit 3
 - May combine Visit 4 and Visit 5 as long as the subject has worn N=145 hours.

6. General Statistical Considerations

6.1 Study Hypothesis

The primary endpoint in this study is 20/20% consistency evaluation with the reference value which is expressed by the agreement rate. Single-armed comparison against target value will be used for the study design, the corresponding hypothesis is:

$$H_0: \mu \leq 60\%$$

$$H_1: \mu > 60\%$$

Where μ represents the expected mean agreement rate for 20/20% consistency evaluation, 60% represents the target rate. The 97.5% lower confidence limit of the mean agreement rate will be tested against corresponding threshold.

6.2 Sample Size Determination

The sample size selected is based on the primary effectiveness endpoint (i.e., accuracy), agreement in comparative readings of paired sensor and YSI glucose readings.

Based on pervious study, using one sample T test (formula provided below) with α level of 0.975 (one sided), β of 0.8, μ_0 is 0.6, μ_α is 0.72 and σ is 0.32:

$$n = \sigma^2 \frac{(t_\alpha + t_\beta)^2}{(\mu_0 - \mu_\alpha)^2}$$

it is indicated that a sample size of 58 will have power greater than or equal to 80% to demonstrate that the overall agreement rate is greater than 0.6. Considering 20% drop out, we need to enroll 72 subjects.

6.3 Analysis Population

Full analysis set (FAS^{#1}): a set of subjects who have a Enlite Sensor inserted.

Full analysis set (FAS^{#2}): a set of subjects who have a Enlite Sensor inserted and have at least one paired Enlite Sensor and YSI measurement.

Per-Protocol Set (PPS) refer to the subgroup population of FAS^{#2} who have no major protocol violations (subjects that violate the inclusion criteria, meet the exclusion criteria, etc.).

Safety Set (SS) will use the same definition method of FAS^{#1}, hence it will not be defined alone in the analysis.

Primary efficacy analysis and secondary efficacy analysis will be analyzed based on both the FAS^{#2} and PPS. All the baseline demographic data and safety evaluation will be analyzed based on the FAS^{#1}.

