10.1. Potential Risks

During the course of the study, risks will be continuously monitored, assessed and documented by the investigators.

Risk with Sensors	Prevention and Mitigation

Risks with Sensors may include:
 
 • Skin irritation or reaction to adhesives • Bruising • Discomfort • Redness • Bleeding • Pain • Rash • Infection • Irritation from tapes used with glucose-sensing products • Raised bump • Appearance of a small "freckle-like" dot where needle was inserted • Allergic reaction • Syncopal episode secondary to needle insertion • Soreness or tenderness • Swelling at insertion site • Sensor fracture, breakage or damage • Minimal blood splatter associated with sensor needle removal • Residual redness associated with adhesive and or tapes • Scarring • Scab • Blister • Itchiness • Inflammation • Anxiety 	
Prevention and mitigation include:
 
 • Follow the provided user guides for insertions and care of sensors. • If a sensor site becomes infected or inflamed, the sensor should be removed and another placed in a new location • Base diabetes management on fingerstick readings
Risks with Serter	Prevention and Mitigation

Risks with Serters may include:
 
 • Improper insertion may lead to device performance issue or hyperglycemia 	
Prevention and mitigation include:
 
 • Follow the provided user guides for insertions and care of Serters. • Training on proper use of the Serter and skin preparation prior to insertion.

CIP313 Clinical Investigation Plan

10688326DOC

Version B

Page 54 of 87

Medtronic

Risks with Finger Sticks	Prevention and Mitigation

Risks with frequent finger stick testing may include:
 
 • Potential risks associated with frequent meter testing of blood glucose include discomfort and ecchymosis at tips of fingers • Potential risks associated with drawing blood include discomfort and bruising 	
Prevention and mitigation include:
 
 • Follow the provided user guides for use of meter with fingerstick testing. • Training on proper use of the meter and fingerstick testing.
Risks with IV Catheter Insertion	Prevention and Mitigation

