11.2. Reporting of Adverse Events

The Investigator or designee will record all AEs while the Subject is enrolled in the clinical study. This includes AE that are device or study procedure related as well as those events with no relationship to the study. Examples include:

- Device related (ADE): insertion site infection
- Serious adverse device effect (SADE): cellulitis at device insertion site requiring hospitalization
- Procedure related AE: bruising at IV insertion site

Subjects participating in the study have diabetes and are expected to experience hypoglycemia and or hyperglycemia. These normal events are not expected to be reported to Sponsor on an AE eCRF as this is not considered an untoward event, but rather an expected occurrence. Any glycemc excursion that meets the protocol definition of Severe Hypoglycemia or DKA is considered an untoward event and a worsening from the subject's baseline and would be reported to Sponsor on an AE CRF.

Adverse events will be documented in the subject source file and reported to sponsor on an eCRF. The Investigational Center is responsible for documentation of AEs including obtaining source documents related to the event, such as emergency medical technician/paramedic reports, hospital records (admission summary; lab results, test results, discharge summary) or device uploads to support the event. Source documents will be reviewed to determine if additional AEs have occurred and require reporting.

Narratives gathered from completed questionnaires will not provide the basis of an AE report however could lead to discussions that result in the identification of a reportable AE.

Adverse events that have not resolved at the time of the subject's discontinuation or completion of the study should have an "outcome" of Not Recovered/Not Resolved at study end in subject source and on an eCRF. The Investigator should ensure that subject is aware of any follow-up or additional treatment that is required for any ongoing AE at end of study participation; however, there will be no eCRF entry for the ongoing follow-up.

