14.6. Analysis Populations, handling of missing data, error

Data entry error or non-reasonable values will be cleaned before data analysis. No imputations will be done for missing data. All enrolled subjects who have at least one paired Enlite Sensor and YSI measurement will be included in the efficacy analysis population. All enrolled subjects who have a Enlite Sensor inserted will be included in the safety analysis population.

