6.4 Analysis Population Set Determination Details

(1) No Enlite Sensor inserted: Subjects obtain randomization number, but have no Enlite Sensor inserted.

(2) No paired Enlite Sensor and YSI measurement: Subjects obtain randomization number and have a Enlite Sensor inserted, but have no paired Enlite Sensor and YSI measurement.

(3) Violation of Inclusion/Exclusion criteria: Subjects do not meet the inclusion criteria or meet the exclusion criteria pre-specified in the protocol, and this protocol deviation may severely affect the results of primary effective endpoint. Whether protocol deviation severely affect the results of primary effective endpoints will be judged together by sponsor, investigators and statistician through discussion;

(4) $FAS^{#1}$ = Number of the randomized subjects – Number of subjects who have no Enlite Sensor inserted;

$FAS^{#2}$ = Number of $FAS^{#1}$ – Number of subjects who have no paired Enlite Sensor and YSI measurement;

PPS = Number of $FAS^{#2}$ - Number of subjects who severely violate study protocol (i.e. violate inclusion and exclusion criteria, etc.).

The listing of subjects who have no Enlite Sensor inserted or severely violate study protocol will be listed, including the center number, registration number, gender, age, type, details, $FAS^{#1}$, $FAS^{#2}$ and PPS.

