7.1 Subject Disposition

The number of subjects enrolled in the study will be presented by study phase. The reasons for discontinuing prior to study completion will be summarized.

- (1) Subjects Enrolled: Subjects who were enrolled in study.
- (2) Screening Failure: The subject did not meet eligibility criteria on visit 1 and did not enter visit 2: randomization. (Is the subject qualified to be randomized into the study collected in CRF was “No”).
- (3) Randomization: The subject entered visit 2: randomization. (Is the subject qualified to be randomized into the study collected in CRF was “Yes”).
- (4) Subjects entering FST: The subject inserted Enlite Sensor successfully and entered visit 4: FST with YSI. (This item is determined based on the subjects’ YSI information).
- (5) Subjects completing Study: Subjects completing Study: The subject completed the last visit. (This item is determined by the section study exit collected in CRF).
- (6) Subjects discontinuing from study phase: The subject did not complete the last visit. (This item is determined by the section study exit collected in CRF).

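### The only safety set requires an inserted sensor, so adverse events recorded before insertion have no place in the analysis and FST-procedure rates may be modestly diluted

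*SAP*

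**What the plan says.** Protocol and SAP agree on who is in the safety analysis. Protocol 14.6: "All enrolled subjects who have a Enlite Sensor inserted will be included in the safety analysis population". SAP 6.3 defines FAS#1 as "a set of subjects who have a Enlite Sensor inserted" and adds no separate safety population: "Safety Set (SS) will use the same definition method of FAS"#1. It then assigns the work: "All the baseline demographic data and safety evaluation will be analyzed based on the" FAS#1. SAP 6.4 gives the count as "Number of the randomized subjects – Number of subjects who have no Enlite Sensor inserted".

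Collection starts earlier. Protocol 8.2 treats a subject as enrolled on signing consent, and Protocol 11.2 says "The Investigator or designee will record all AEs while the Subject is enrolled in the clinical study". Protocol 9.2.2 places a blood draw for hematocrit and A1C at Visit 1. Among the risks listed in Protocol 10.1 are faintness, bruising and infection with blood draws, and "Syncopal episode secondary to needle insertion" with sensors.

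On the FST, Protocol 9.2.5 describes the session as IV sampling, and Table 2 allows it to begin no earlier than 1 hour after insertion. SAP 7.1(4) counts a disposition group: "Subjects entering FST: The subject inserted Enlite Sensor successfully and entered visit 4: FST with YSI". SAP 7.10 lists procedure-related AEs as one category and gives no denominator by type of event.

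**The concern.** A safety set should match exposure to the harms it is used to describe. Here there are three gaps.

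- **Before insertion.** An AE after the screening blood draw in someone who never receives a sensor is recorded but belongs to no analysis set. This sits uneasily with Protocol 9.13, which says data up to a subject's exit will be used, and with SAP 6.5, which brings all withdrawn subjects into the final analysis.
- **At insertion.** The word inserted is not defined for a failed or abandoned attempt. If such an attempt were read as not inserted, membership of the safety set could depend on the harm itself, for example a faint that ends the attempt.
- **After insertion.** Events caused by the IV line or the FST can arise only in subjects who start that procedure, but the one available denominator is everyone with a sensor.

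Safety is part of the stated study purpose (Protocol 4.2). In a trial of this size, one omitted event is visible in the report.

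**Working it through.** **The plan's own figures.** The documents give no safety rate and no expected size for the safety set. The relevant counts are 58 evaluable subjects and 72 enrolled (Protocol 14.5, SAP 6.2), and about 60 completers (SAP 5.1). The 58 reproduces: for a one-sample t test at one-sided 0.025 with means 0.60 and 0.72 and SD 0.32, power is 80.2% at n = 58 and 79.5% at n = 57. Allowing for 20% drop-out, 58 / 0.8 = 72.5, against the stated 72. This checks the counts only; it has no bearing on the safety set itself.

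**Who is in and who is out.**

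| Subject | AEs recorded? | In FAS#1? |
|---|---|---|
| Screen failure after the Visit 1 blood draw | Yes (8.2, 11.2) | No |
| Randomised, no insertion attempted | Yes | No |
| Randomised, insertion failed or abandoned | Yes | Not stated |
| Sensor inserted, left before the FST | Yes | Yes |
| Sensor inserted, entered the FST | Yes | Yes |

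The first two rows follow from the text. The third is an ambiguity. The number of AEs in these rows cannot be computed, because the documents give no event rates. As a hypothetical illustration only: if insertion were attempted in 72 subjects, and one fainted, left without a sensor and was read as not inserted, the report would show 0/71 rather than 1/72 (1.4%).

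**Dilution of FST/IV rates.** Let N be the size of FAS#1, f the number who entered the FST, and x the number with an FST/IV event. The rate over FAS#1 is x/N and the rate among those exposed is x/f. The relative understatement is 1 − (x/N)/(x/f) = 1 − f/N.

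| N | f | 1 − f/N | Example, x = 6: x/N against x/f |
|---|---|---|---|
| 72 | 72 | 0% | 8.3% against 8.3% |
| 72 | 60 | 16.7% | 8.3% against 10.0% |
| 72 | 58 | 19.4% | 8.3% against 10.3% |

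The last two rows are upper bounds. They assume that all 72 enrolled subjects receive a sensor and that all drop-out falls between insertion and the FST. Enrolment is counted from consent, so screen failures may use up part of the 72 without entering FAS#1. If, say, 6 of the 72 were never inserted (an assumption), N = 66 and 1 − 60/66 = 9.1%. Subjects who leave after their FST cause no dilution, and Day 1 subjects have theirs within 25 hours of insertion.

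**The case against.** The strongest defence is that a device-exposed set is the natural one for device-related AEs, that protocol and SAP agree on it, and that safety is descriptive. That stands, and it is why FAS#1 should remain the main set.

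Other outputs also cover part of the gap. SAP 6.4 lists subjects with no sensor inserted, SAP 7.1 summarises reasons for discontinuation, SAP 7.3 reports insertions for every enrolled subject, and device deficiencies are summarised separately in SAP 7.11. SAE reporting and review by the clinical events committee are not limited to FAS#1. This stands in part: the SAP 6.4 listing names no AE field, and none of these outputs reports non-serious AEs outside FAS#1.

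On dilution, the defence is that SAP 7.10 fixes no denominator by event type, that the table shells are in an appendix not available here, and that a reader could rescale using the FST count. But SAP 6.3 gives the whole safety evaluation to FAS#1, so that is the natural reading. Rescaling also works only if FST/IV events are shown apart from other procedure-related AEs, which the SAP does not promise.

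A reader might infer more than the documents support:

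- **IV harm in subjects who never have a sensor is dropped.** Under the schedule this does not arise, since the FST follows insertion by at least 1 hour. A line placed before insertion in a Day 1 subject is not described anywhere.
- **Insertion harms are excluded by rule.** They are not. The population definition does not require success; that word appears only in the FST disposition count. Each subject also receives two sensors, so exclusion would require that neither counted as inserted.
- **Glucose excursions belong to the FST denominator.** Ordinary hypo- and hyperglycaemia are not reported as AEs (Protocol 11.2), and severe hypoglycaemia or DKA can occur at any time while enrolled.
- **Every gap flatters the device.** Leaving out never-inserted subjects who had no event shrinks the denominator and raises rates.

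**Conclusion.** The point holds as a limited reporting gap. It is certain from the text that AEs in screen failures and in randomised subjects with no insertion attempt are recorded but fall outside the only safety set; how many there would be is unknown. It is unresolved whether a failed or abandoned insertion counts. The understatement of FST/IV procedure-related rates lies between 0% and about 17–19% in relative terms. The upper end rests on all 72 being inserted and all drop-out falling before the FST, and on FAS#1 being the denominator used. It should not be read as the expected size. Success is decided on the primary endpoint alone (Protocol 14.9), so no conclusion of the trial changes. This is a minor improvement, worth making because it is cheap.

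**What to change.** 1. Keep FAS#1 as the main set for device- and wear-related AEs.
2. In SAP 6.3/6.4 and Protocol 14.6, state that any attempted insertion counts as inserted.
3. Add a listing of all AEs from consent onwards for subjects outside FAS#1, including those after the screening blood draw. This also brings the safety reporting into line with Protocol 9.13.
4. In SAP 7.10, show FST/IV procedure-related AEs separately and also report them over the subjects counted in SAP 7.1(4). Do not apply that denominator to severe hypoglycaemia or DKA occurring outside the FST.

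An IV-placement criterion for the safety set is not needed.

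The cost is a few sentences, one listing and one extra denominator, all from data already collected. Some stated rates may become slightly less favourable.
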